Improving Preterm Infant Outcomes with Family Integrated Care and Mobile Technology

ID: 16-19542

Study Protocol and Statistical Analysis Plan

January 17, 2018

Study Protocol

Study staff at UCSF, UCLA, BCH-O, and CRMC will perform the following procedures.

Usual FCC Group:

Education: Parents will receive an orientation to the unit by a NICU nurse and will have access to the usual written and video materials provided by the NICU. Parents will receive all NICU-required individualized parent teaching and support, delivered at the bedside by nurses or the Discharge Coordinator.

Direct care: Parents will be encouraged by nurses to participate in infant care under nursing supervision for feeding, bathing, dressing, and holding skin-to-skin.

Social work and other support: Individualized support from social workers, lactation consultants and other specialists will be offered.

Documentation: Parents will not be asked to formally document any observations of their infant or their own skills acquisition. Nurses and Discharge Coordinators will complete the standard Discharge Teaching Checklist per usual hospital policies. Parents will be asked to track their time in the NICU, time learning from nurses and time spent in infant caregiving activities, and to keep a journal of their NICU experience (without any specific instructions about content). They will use the We3Health App for this, with only the data tracking and journal features activated. These data will not be shared with the clinical team.

mFI-Care Group:

mFI-Care clinical team and alumni parent training: After completion of the usual FCC group enrollment, nurses who volunteer to provide care to mFI-Care infants/parents and the volunteer alumni parents will receive in-person and online training from the study team. The nurse training will follow the Canadian FI-Care curriculum and cover topics such as the differences between FCC and mFI-Care, psychological implications of preterm birth for parents, infant development, parent-infant attachment, re-conceptualization of the nursing role, and parent coaching skills. Alumni parent training will follow the Canadian FI-Care curriculum. Physicians, therapists and social workers will receive in-person and online inservice education specific to their roles. Once training and inservice education are complete, mFI-Care enrollment will commence.

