Descriptive statistics will be provided for all study variables: means and standard deviations for quantitative variables and frequencies and percents for categorical variables. Data analysis will be based on an intention-to-treat strategy with all participants enrolled in the usual FCC or mFI-Care groups at UCSF analyzed within their respective groups regardless of compliance with the group assignment. Outcomes will be compared between the usual FCC and mFI-Care groups using t-tests for continuous variables, Wilcoxon tests for ordinal variables, and chi-square tests for categorical variables. We expect 225 eligible ICN admissions during the study period and anticipate enrolling 50 parent-infant pairs in each group (usual FCC and mFI-Care) at UCSF. Assuming 20% attrition, we will have complete data on 40 infants per group. Enrollment at the UCLA site is exploratory to further assess feasibility and acceptability thus statistical power is based on the UCSF sample. The primary outcome, change in weight Z-score, typically has a standard deviation of between 0.44-0.47 (data from Toronto pilot and Canada-led cRCT). With a 0.05 null-hypothesis rejection threshold (alpha) for the two-tailed t-test, we will have 80% power to identify a group difference of 0.28-0.29. Differences among the groups in potential confounding variables (e.g., GA, birth weight) will be examined. Variables that differ among the groups may be considered as covariates when examining group differences in the primary and secondary outcomes. The covariate-adjusted scores may provide more precise estimates of the effect sizes. We will calculate confidence intervals around the differences because this will give a better idea of the range of values around the true means for the population and guide the sampling strategy for the future US cRCT. We will compare participation rates in specific aspects of usual FCC and mFI-Care such as caregiving activities, education, time spent with the infant or holding skin-to-skin or the primary and secondary outcome variables to see if they differ for parents and infants with different characteristics (e.g., sex, race/ethnicity or distance between hospital and home). We will compare attitudes and perceived practices of nurses and physicians during the FCC and mFI-Care conditions.

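### The two UCSF groups are enrolled consecutively, but the stated comparison is an unadjusted t-test and adjustment for GA and birth weight is left optional

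*Combined protocol and SAP*

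**What the plan says.** The Study Protocol (mFI-Care Group, paragraph on training the clinical team and alumni parents) fixes the order of enrolment. Training follows the first cohort: "After completion of the usual FCC group enrollment, nurses who volunteer to provide care to mFI-Care infants/parents" are trained at that point. Then: "Once training and inservice education are complete, mFI-Care enrollment will commence". The documents describe no randomisation.

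The Statistical Analysis Plan states the comparison: "Outcomes will be compared between the usual FCC and mFI-Care groups using t-tests for continuous variables". Alpha and power are attached to the same unadjusted test: "for the two-tailed t-test, we will have 80% power to identify a group difference of 0.28-0.29". Power rests on the UCSF sample alone.

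On confounding it says: "Differences among the groups in potential confounding variables (e.g., GA, birth weight) will be examined". The rule for acting on what is found is: "Variables that differ among the groups may be considered as covariates when examining group differences in the primary and secondary outcomes". The only benefit it gives for adjustment is precision: "The covariate-adjusted scores may provide more precise estimates of the effect sizes". The confidence intervals are meant, among other things, to "guide the sampling strategy for the future US cRCT".

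**The concern.** With consecutive cohorts, group and calendar phase coincide at UCSF. Nothing in the design balances GA, birth weight or anything else between phases, so adjustment is needed to limit bias and not only to gain precision. The plan makes it conditional on an undefined observed difference, and optional even then. It does not say whether the adjusted or unadjusted result is primary, so two analysts following it could report different primary results.

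There are two ways to read it:

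- **The t-test is primary (the natural reading).** Any phase shift in GA or birth weight that is related to weight gain goes straight into the estimate.
- **Adjustment is triggered by an observed imbalance.** With 40 infants per group, a modest shift will usually go unflagged and uncorrected.

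Either way, a case-mix shift could be carried into planning of the later cluster trial as though it were an mFI-Care effect. The plan does not say whether the interval used for that purpose is adjusted.

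**Working it through.** **Inputs from the Statistical Analysis Plan.** 50 enrolled per group; 20% attrition, so 50 × 0.8 = 40 analysed per group; SD 0.44-0.47; two-sided alpha 0.05; power 80%.

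**Assumptions, not in the documents.** One measured linear confounder with correlation r = 0.3-0.5 with the outcome; a phase shift d of 0.1-0.5 SD in that confounder; no true mFI-Care effect; SD 0.455 (midpoint of the stated range). The threshold for a difference is also assumed: p<0.05, with p<0.20 as a variant.

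**Step 1: the plan's own figure.** Detectable difference = SD × √(2/40) × (1.960 + 0.842).

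- SD 0.44: 0.44 × 0.2236 × 2.802 = 0.276
- SD 0.47: 0.47 × 0.2236 × 2.802 = 0.294

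This reproduces the stated 0.28-0.29. The exact t calculation gives 0.279-0.298, and 0.289 at SD 0.455. The power figure is sound for an unadjusted test and is not in dispute.

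**Step 2: chance that a shift is noticed.** A two-sample t-test on the confounder (78 df, noncentrality d/√(2/40)) reaches p<0.05 in 7%, 14%, 26% and 60% of trials at d = 0.1, 0.2, 0.3 and 0.5. An 80% chance needs a shift of 0.63 SD.

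**Step 3: bias of the unadjusted difference.** Bias = d × r × SD.

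- d = 0.3, r = 0.3: 0.3 × 0.3 × 0.455 = 0.041 (0.041/0.289 = 14% of the detectable difference)
- d = 0.5, r = 0.5: 0.5 × 0.5 × 0.455 = 0.114 (0.114/0.289 = 39%)

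**Step 4: simulation of the possible rules.** 200,000 trials per setting. Each cell gives bias in Z, then type I error.

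| r | d | t-test | adjust if p<0.05 | adjust if p<0.20 | always adjust |
|---|---|---|---|---|---|
| 0.3 | 0.1 | 0.013, 5.1% | 0.009, 4.8% | 0.004, 4.5% | 0.000, 4.9% |
| 0.3 | 0.2 | 0.028, 5.9% | 0.017, 5.1% | 0.008, 4.7% | 0.000, 5.0% |
| 0.3 | 0.3 | 0.041, 6.9% | 0.020, 5.3% | 0.008, 4.8% | 0.000, 5.0% |
| 0.3 | 0.5 | 0.068, 10.1% | 0.016, 5.4% | 0.004, 5.0% | 0.000, 5.0% |
| 0.5 | 0.1 | 0.023, 5.5% | 0.016, 4.5% | 0.007, 3.9% | 0.000, 5.0% |
| 0.5 | 0.2 | 0.045, 7.3% | 0.028, 5.1% | 0.012, 4.2% | 0.000, 5.1% |
| 0.5 | 0.3 | 0.069, 10.2% | 0.034, 5.6% | 0.013, 4.5% | 0.000, 5.0% |
| 0.5 | 0.5 | 0.114, 19.7% | 0.026, 6.0% | 0.007, 4.9% | 0.000, 5.0% |

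Under the p<0.05 rule about 69%, 62%, 50% and 23% of the unadjusted bias remains at d = 0.1, 0.2, 0.3 and 0.5. Taking whichever of the two models gives the smaller p-value adds 1.4-2.5 percentage points to the t-test's type I error (for example, 6.4% against 5.0% at r = 0.3 with no shift).

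**Step 5: two confounders.** With mutual correlation 0.5-0.8, both shifted and each with r = 0.3-0.5 (40,000 trials), the p<0.05 rule gives 4.4-5.6% type I error and residual bias of 0.009-0.034 Z. Always adjusting gives 4.9-5.2%.

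**Step 6: what adjustment cannot do.** With no measured shift but an assumed unmeasured period effect of 0.05 Z, type I error is 8.1-8.6% with fixed adjustment and 7.7-7.9% with the t-test. At 0.10 Z it is 16.9-20.2% and 16.0-16.2%.

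**The case against.** The plan is not blind to confounding. It commits to examining GA and birth weight, provides for adjusted analyses and promises confidence intervals. It sets no p<0.05 threshold, so a reader could treat any meaningful difference as a trigger. Under a p<0.20 rule the residual bias is only 0.004-0.013 Z, under 5% of 0.289. Even under p<0.05, residual bias of 0.009-0.034 Z (3-12% of 0.289) is small beside a 95% interval half-width of about 1.99 × 0.455 × 0.2236 = 0.20 Z. The larger figures require that nobody adjusts after a sizeable shift. The zero bias under fixed adjustment follows from simulating one correctly measured linear confounder. Adjusting a change score for something close to its baseline can also introduce bias in non-randomised groups (Lord's paradox). Finally, the intervals are to inform sampling for a later trial; the plan does not say the point estimate will be its planning effect.

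Much of this stands as a limit on size. The sensitivity to the trigger is real and the correlation and shift are assumed. It does not remove the point. The plan states neither threshold, its wording permits no adjustment at all, and even the looser rule leaves some bias. The Lord's paradox concern carries little weight here, because group is set by calendar phase and the plan itself treats these variables as potential confounders.

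**Conclusion.** The concern holds. The UCSF comparison is a non-randomised before-after contrast whose stated test ignores confounders the plan names, and the adjustment rule is undefined and non-binding. This should be fixed, but it does not invalidate the study.

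Its size depends on the reading and on the assumed correlation and shift. With the t-test as primary, the effect is minor at shifts of 0.1-0.2 SD and material at 0.3-0.5 SD. With a significance-triggered rule, type I error is close to nominal (4.5-6.0%) and the remaining problem is a modest bias. Confidence is medium, because the documents allow no check of either assumption.

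**What to change.** 1. Make the primary analysis a linear regression of change in weight Z-score on group, GA and birth weight, with both covariates included whether or not they differ. Name any further covariates before group outcomes are compared. Report the t-test as supportive.
2. Base the confidence interval used for the future cluster trial on the adjusted estimate.
3. Describe the UCSF result as a non-randomised before-after difference, and state that adjustment covers measured confounding only and cannot separate mFI-Care from a period effect.

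The cost is SAP wording; the plan already examines GA and birth weight. With 80 infants and four coefficients, 80 − 4 = 76 degrees of freedom remain. The effect on precision, assuming a correlation of 0.5-0.8 between the two covariates and including chance imbalance, is:

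| Covariate relation to outcome | Shift | Change in SE | Detectable difference (from 0.289) |
|---|---|---|---|
| None | Equal, up to 0.3 SD | +1 to +3% | 0.293-0.297 |
| None | Both 0.5 SD | +5 to +6% | 0.303-0.305 |
| None | Only one, 0.5 SD | +6 to +10% | 0.305-0.318 |
| r = 0.3-0.5 each | Equal, up to 0.3 SD | −3 to −17% | 0.239-0.281 |
| r = 0.3 each | Only one, 0.5 SD | up to +4% | up to 0.301 |
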